5.7.7.8. Common TEAE by intrinsic factor

Summary of common TEAE and PT having the word “Vertigo” (defined in Section [5.7.7.7](#)) will be created by the following groups

- Gender: male/female
- Age: [Age<30] [30<=Age<50] [50<=Age<65] [65<=Age]
- BMI: [BMI <18.5] [18.5<=BMI<25] [25<=BMI<30] [30<=BMI]
- CVRF: [CVRF =0] [CVRF =1] [CVRF =2] [CVRF =3] [4<=CVRF]

Note: CVRF is defined in Section [5.8](#).

5.7.7.9. TEAE by Extrinsic Factor

Summary of TEAE (SOC/PT) will be created for each of these users:

- Heart Rate Lowering Medications
- Serotonergic Medications
- Contraceptives
- Non-steroidal anti-inflammatory Drugs
- CNS Sedating Medications
- Chinese Medicine

The definitions are medically reviewed before the DBL.

The summary of medication names for each of the above category will be created.

5.8. Subgroup Analysis

Subgroup analysis is summarized in [Table LAIH. 5.6](#).

- For efficacy analyses based on proportion, the logistic regression used in [T1] will be applied to each subgroup separately. The model term includes treatment and baseline usage of preventive medications to reduce the frequency of migraine (Yes/No). The odds ratio (relative to placebo), its 95% confidence interval, and p-value will be calculated based on this model.
- For efficacy analyses based on proportion, additional logistic regression will be used. The model term includes treatment, baseline usage of preventive medications to reduce the frequency of migraine (Yes/No), subgroup, and treatment-by-subgroup interaction. The p-value for treatment-by-subgroup interaction will be displayed. The level of significance for interaction (2-sided test) is defined as 0.05 (See Section [5.4](#)).
- For efficacy analyses based on continuous variables, ANOVA will be used for each subgroup separately. The model includes treatment and baseline usage of preventive medications to reduce the frequency of migraine (Yes/No). Change from baseline and p-values for treatment comparison will be calculated.
- For efficacy analyses based on continuous variables, additional ANOVA will be used for The model includes treatment, baseline usage of preventive medications to reduce the frequency of migraine (Yes/No), subgroup, and treatment-by-subgroup interaction. The p-value for treatment-by-subgroup interaction will be displayed. The level of significance for interaction (2-sided test) is defined as 0.05.

Table LAIH. 5.6 Subgroup Analysis

ID	Type	Analysis population [Note 1]	Dmg	PF/PR/ MBS/ Disa. at 2h	PGI-C at 2h/24h, Satisf. at 48 h	TEAE by PT	Other Analysis
SUB1	Triptan responder vs. insufficient responder (based on the most recent triptan experience)	mITT and patients who has triptan experience in lifetime	O		O	O	[1] PF/PR/MBS/disability time course (up to 48 hours) [2] EQ-5D-5L at 24h [3] Triptan detail summary at baseline

ID	Type	Analysis population [Note 1]	Dmg	PF/PR/ MBS/ Disa. at 2h	PGI-C at 2h/24h, Satisf. at 48 h	TEAE by PT	Other Analysis
SUB2	TEAE-Dizziness regardless of causality (with/without)	mITT	O	O	O	O	[1] Extended Demographic -- continuous -- vital (SBP, DBP, HR) at baseline -- categorical -- Severity of migraine attack (at 0 hour) (Mild/Moderate/Severe) At least 1 CVRF (Yes/No) Valproic acid use (on Visit 2) (Yes/No) Lomerizine use (on Visit 2) (Yes/No) Amitriptyline use (on Visit 2) (Yes/No)
SUB3	Menstrual related (yes/no)	mITT	O			O	PF/PR/MBS/disability time course (up to 48 hours)
SUB4	Body weight	mITT	O	O	O	O	
SUB5	Baseline migraine disability (need complete bed rest vs others)	mITT		O			
SUB6	Baseline headache (severe vs moderate)	mITT		O			
SUB7	Aggressive headache	mITT		O			
SUB8	Time to dose	mITT		O		O	
SUB9	Time dosed (4am-8am vs other time)	mITT		O			
SUB10	Tension type headache (Yes/No)	mITT	O	O		O	
SUB11	Mood and Anxiety disorders (Yes/No)	mITT	O	O		O	
SUB12	CVRF(CVRF<=1 vs 2<=CVRF)	mITT	O	O		O	

ID	Type	Analysis population [Note 1]	Dmg	PF/PR/ MBS/ Disa. at 2h	PGI-C at 2h/24h, Satisf. at 48 h	TEAE by PT	Other Analysis
SUB13	Patients who use migraine prevention therapy during the study.	mITT	O	O		O	
SUB14	Migraine with aura (Medical History) (with/without)	mITT	O	O			
SUB15	Gender	mITT	O	O		O	
SUB16	Age	mITT	O	O		O	
SUB17	Rescue or Recurrence Medication Use	NA				O	
SUB18	Triptan users within 3 months of informed consent (yes/no)	mITT	O		O	O	[1] PF/PR/MBS/disability time course (up to 48 hours) [2] EQ-5D-5L at 24h
SUB19	TEAE-Somnolence regardless of causality (with/without)	mITT	O	O	O		
SUB20	Triptan naïve vs. experienced (ever)	mITT	O		O	O	[1] PF/PR/MBS/disability time course (up to 48 hours) [2] EQ-5D-5L at 24h [3] Triptan detail summary at baseline
SUB21	Pain Freedom over Time	mITT					[1] Percent of patients with no disability by pain freedom (yes versus no) over time

Abbreviation of the column headers:

Dmg= Demographics; PF/PR/MBS/Disa. at 2h= Pain free, Pain Relief, MBS-Free, and Disability at 2 hours analysis (based on analysis in [Table LAIH. 5.3](#)); PGI-C at 2h/24h, Satisf. at 48 h= PGI-C analysis at 2 hours and 24 hours, and Treatment Satisfaction at 48 hours (based on analysis in [Table LAIH. 5.3](#)).

Abbreviations: CVRF = Cardiovascular Risk Factor; DBP = Diastolic blood pressure; EQ-5D-5L = EuroQol 5-dimension 5-level scale; h= hour; HR = Heart rate; ITT = intent-to-treat population;

MBS = the most bothersome symptom; mITT = modified intent-to-treat population; NA = not applicable; PGI-C = Patient Global Impression of Change; SBP = Systolic blood pressure; TEAE = Treatment emergent adverse event.

Note 1: Safety analysis (TEAE by PT) will be based on safety population. For SUB1, it is based on safety population and patients who has triptan experience in lifetime.

Definitions for each subgroup are as follows:

SUB1: Triptan responder vs. insufficient responder (based on the most recent triptan experience)

Group 1: Triptan responder: patients having experience of triptan but not in the group 2

Group 2: Triptan insufficient responder: patients who satisfy one of the conditions below d.i-d.vi

In this subgroup analysis, detailed summary of triptan usage at baseline will be created. The descriptive statistics of the response to triptans, the discontinuation reasons, and following summaries are created:

- a. Summarize n (%) with triptan experience (by Visit 1)
- b. Summarize number of current/prior triptans per patient, mean (range) (by Visit 1)
- c. Summarize number patients who used triptans within 3 months
- d. Summarize triptan insufficient responders in using each method: (by Visit 1)
 - i. Overall response none/poor (based on most recent triptan, either ongoing [start date <= V1 and ongoing or if no ongoing triptan, most recent]) (most recently used triptans)
 - ii. Inconsistent response (based on most recent triptan, either ongoing [start date <= V1 and ongoing or if no ongoing triptan, most recent])
 - iii. Triptan discontinuer

Note: Reason for discontinuation is captured in CRF. The triptan discontinuer is defined for those patients who choose one of the followings:

- “Lack of pain freedom at 2 hours”,
- “Lack of pain relief at 2 hours”,
- “Did not return function or eliminate disability”,
- “Inconsistent response”,
- “Migraine recurrence”,
- “Intolerance to Medication”,
- “Did not relieve associated symptoms”,

“Did not like route of administration”,
“Discontinued due to cardiovascular disease or event”,
“Discontinued due to cardiovascular risk factors”,
“Discontinued due to contraindication or warning”.

iv. mTOQ poor response (based only on ongoing most recent triptan – Current Triptan users Patients who have a score of poor or very poor using the mTOQ). The definition is based on [mTOQ-6 Conversion Method 2] in Section 5.5.3.

v. Composite triptan insufficient responder (satisfying at least one of [ii], [iii], or [iv])

vi. Triptan Contraindicated patients. Defined as patients who have at least one of the following SMQ terms (Narrow Scope PT):

- Angina pectoris
- Angina unstable
- Myocardial infarction
- Acute myocardial infarction
- Silent myocardial infarction
- Myocardial ischaemia
- Coronary artery disease
- Microvascular coronary artery disease
- Arteriosclerosis coronary artery
- Wolff-Parkinson -White syndrome
- Arrhythmia
- Cerebrovascular accident
- Embolic stroke
- Ischaemic stroke
- Transient ischaemic attack
- Peripheral vascular disorder
- Raynaud's phenomenon
- Superior mesenteric artery syndrome
- Labile hypertension
- Prinzmetal angina
- Cerebrovascular disorder
- Malignant hypertensive heart

SUB2: TEAE-Dizziness regardless of causality (with/without)

Group 1: Patients with TEAE Dizziness regardless of causality

Group 2: Otherwise.

SUB3: Menstrual related (yes/no)

Group 1: Female with menstruation at least one day in [Day(-2), Day(-1), Day 1, Day 2, Day 3] of dosing.

Group 2: Otherwise.

Note: Day 1 is the day when a patient takes the treatment. Day(-1) is one day before Day 1.

SUB4: Body weight

Group 1: weight <=median

Group 2: median < weight

SUB5: Baseline migraine disability (need complete bed rest vs others)

Group 1: Patients who has Baseline (0 hour) migraine disability (need complete bed rest)

Group 2: Otherwise.

SUB6: Baseline headache (severe vs moderate)

Group 1: Patients who has Baseline (0 hour) headache severity= severe.

Group 2: Otherwise.

SUB7: Aggressive headache

Group 1: Patients who satisfy both [Condition 1] and [Condition 2]:

[Condition 1] Dosing time – Migraine onset <=1hour

[Condition 2] Baseline severity=severe

Group 2: Otherwise.

SUB8: Time to dose

Based on dosing time and onset of migraine, 2 groups are defined as follows:

Group 1: dosing time <1 hour

Group 2: 1 hour <= dosing time

SUB9: Time dosed (4am-8am vs other time)

Group 1: Patients who has dosing in the morning, [4am<=dosing <=8am]

Group 2: Otherwise.

SUB10: Tension type headache (Yes/No)

Group 1: Patients who has PT= [Tension headache] as comorbid condition

Group 2: Otherwise.

SUB11: Mood and Anxiety disorders (Yes/No)

Group 1: Patients who has following PT as medical history,

Agitated depression, Childhood depression, Depression, Depression suicidal, Menopausal depression, Major depression, Perinatal depression, Persistent depressive disorder, Depressed mood, Depressive symptom, Mixed anxiety and depressive disorder, Anxiety disorder, Social anxiety disorder, Anxiety, Generalized anxiety disorder, Bipolar disorder, Bipolar I disorder, Bipolar II disorder

Group 2: Otherwise.

SUB12: CVRF(CVRF<=1 vs 2<=CVRF)

Group 1: Patients with CVRF <=1

Group 2: Patients with CVRF >=2

Note: The CVRF is defined as follows. (Reference: Comprehensive risk management chart for cerebro-cardiovascular disease 2019; The Japan Society of Internal Medicine (Vol.104-4))

CVRF1: Current smoker at baseline (Visit 1)

CVRF2: Hypertension, patients having condition at baseline (Visit 1) below a) or b)

- a) Narrow terms in Hypertension (SMQ 20000147)
- b) Baseline blood pressure is systolic >=140mmHg, or diastolic >=90mmHg

CVRF3: Diabetes at baseline (Visit 1) (including impaired glucose tolerance, patients having condition below a) or b)

a) Comorbidity PT: Diabetes mellitus, Type 1 diabetes mellitus, Type 2 diabetes mellitus, Latent autoimmune diabetes in adults, Hyperglyceridaemia, Cataract diabetic, Diabetic nephropathy, Diabetic autonomic neuropathy, Diabetic retinopathy, Impaired glucose tolerance

b) Baseline blood sugar level, non-fasting Glucose >=200 mg/dl

CVRF4: Dyslipidemia, patients having condition at baseline (Visit 1) below:

Comorbidity PT: Hypercholesterolaemia, Hyperlipidaemia, Dyslipidaemia, Type IIa hyperlipidaemia, High density lipoprotein decreased, Low density lipoprotein increased, Metabolic syndrome, Hypertriglyceridaemia.

CVRF5: Chronic kidney disease (only Comorbidity PT term) at baseline (Visit 1)

CVRF6: Obesity (BMI >=25) at baseline (Visit 1)

CVRF7: Age at baseline (Visit 1)

Male patients: age >=45 years old,

Female patients: age >=55 years old,

CVRF8: Gender, patients below a) or b)

- a) Male
- b) Postmenopausal female (defined in [Table LAIH. 5.7](#))

Table LAIH. 5.7 Definition of Postmenopausal female

Baseline FSH	Menstrual Period Question in CRF (YES/NO)	Postmenopausal?
FSH >40mIU/mL	NO	YES
FSH >40mIU/mL	YES	YES
FSH <=40mIU/mL or missing	NO	YES
FSH <=40mIU/mL or missing	YES	NO

Abbreviation: CRF = case report form FSH = follicle-stimulating hormone.

CVRF9: Family (Parents, Grandparents, and siblings) history of CVD (Yes for Coronary artery disease, Cardiovascular disorder, or Cerebrovascular disorder in eCRF “Associate Person Medical History: Special Interest”)

SUB13: Patients who use migraine prevention therapy during the study.

Note: This is based on CRF, not IWRS.

Group 1: Patients who use migraine prevention therapy

Group 2: Otherwise.

SUB14: Migraine with aura (Medical History) (with/without)

Group 1: Patients having migraine with aura in medical history.

Group 2: Otherwise

SUB15: Gender

Group 1: Male

Group 2: Female

SUB16: Age

Group 1: Age <=median

Group 2: median < Age

SUB17: Rescue or Recurrence Medication Use

Patients who use rescue or recurrent medication at specific time (0 hour is dosing time) defined below.

Group 1: 0 hour <= medication use <=2 hour

Group 2: 2 hours < medication use <=24 hour

Group 3: 24 hours < medication use <=48 hours

Note: Patients can be in multiple groups.

SUB18: Triptan users 3 months prior to informed consent (yes/no)

Group 1: Patients who used at least one triptan within 3 months of informed consent.

Group 2: Otherwise

SUB19: TEAE-Somnolence regardless of causality (with/without)

Group 1: Patients who has at least one TEAE-Somnolence regardless of causality

Group 2: Otherwise.

SUB20: Triptan naïve vs. experienced (ever)

Group 1: Triptan experienced = patients who has triptan experience in lifetime

Group 2: Otherwise.

SUB21: Pain Freedom over Time

At each postbaseline time point, subgroup is defined as

Group 1: Patients who achieved pain freedom at the time point.

Group 2: Otherwise.

Percent of patients with no disability by pain freedom (yes versus no) over time will be displayed. There is no statistical test. Missing data were excluded from the analysis at each time point. For patients who took rescue medication, data were also excluded.

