5.7. Safety Analyses

The safety and tolerability of treatment will be assessed by the followings:

- Adverse events
- Suicide-related thoughts and behaviors
- Vital signs and weight
- Laboratory measurements
- ECGs
- Assessment of Driving Incidents

For vital signs, weights, and labs, the baseline value is defined as the last non-missing value before or at Visit 2.

The post-baseline value is defined as the last measurement on EoS/Visit 3. Note that this study does not have any unscheduled visit and associated measurement. Therefore, there is only one post-baseline values. However, if there are multiple post-baseline values, then the last measurement on EoS/Visit 3 will be used for continuous analysis and all values after dosing will be considered as post-baseline values for categorical analysis.

5.7.1. *Adverse Events*

AEs will be coded by the latest Medical Dictionary for Regulatory Activities (MedDRA) version at the timing of the final DBL.

AEs are collected from Visit 1 to Visit 3.

An AE with the time of onset on or within 48 hours after a dose of study drug, or an event that worsens in intensity within 48 hours of a dose of study drug will be considered a treatment-emergent adverse event (TEAE).

Post-dose AEs are defined as the same as the TEAE except without the restriction of the 48 hours cutoff.

For each TEAE, the reported severity of the event (mild, moderate, or severe) will be determined by physicians. The Medical Dictionary for Regulatory Activities (MedDRA) Lowest Level Term (LLT) will be used in the treatment-emergent computation. For each patient and TEAE, the maximum severity for the MedDRA level being displayed (preferred term, High Level Term,

or system organ class [SOC]) is the maximum postbaseline severity observed from all associated LLTs mapping to that MedDRA level.

Serious Adverse Events (SAE) are defined in PROTOCOL Section 9.2.1.

Treatment Emergent SAE (TESAE) is an SAE which occurs within 48 hours after a dose of study drug.

Following summary will be created:

- Overview of AEs (including death, SAE, TESAE, Discontinuations from Study due to an Adverse Event, AE, post-dose AE, TEAE, TEAE related to study treatment)
- TEAEs
 - By PT by decreasing frequency
 - By PT by decreasing frequency with an incidence in any lasmiditan group $\geq 1.5\%$ (common TEAE) and PT including “Vertigo”.
 - By SOC/PT (sorted alphabetically by system organ class (SOC), then by frequency in preferred term (PT))
 - By maximum severity/PT

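### SUB2 and SUB19 test lasmiditan against placebo within groups defined by dizziness or somnolence after dosing, so these contrasts are not randomised comparisons

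*SAP*

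**What the plan says.** SAP Section 5.8 defines SUB2 as "Group 1: Patients with TEAE Dizziness regardless of causality" against everyone else, and SUB19 as "Group 1: Patients who has at least one TEAE-Somnolence regardless of causality" against everyone else. Table LAIH. 5.6 marks both, in the mITT population, for pain freedom, pain relief, MBS freedom and disability at 2 hours, and for PGI-C and treatment satisfaction.

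The general rules of Section 5.8 then apply. For proportions, "the logistic regression used in [T1] will be applied to each subgroup separately", and "The odds ratio (relative to placebo), its 95% confidence interval, and p-value will be calculated based on this model". A second model adds subgroup and treatment-by-subgroup terms: "The p-value for treatment-by-subgroup interaction will be displayed", and "The level of significance for interaction (2-sided test) is defined as 0.05". Neither SUB2 nor SUB19 has an exemption or a caveat.

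SAP Section 5.7.1 sets the TEAE window: "An AE with the time of onset on or within 48 hours after a dose of study drug", or worsening within that time. Protocol Section 5.4 states that TEAEs were more frequent on lasmiditan than on placebo, lists dizziness and somnolence among the commonest, and says that they generally rose with dose.

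SUB21 groups patients by pain freedom achieved after dosing and displays disability within those groups. For it the SAP says: "There is no statistical test".

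**The concern.** Randomisation makes the arms comparable at dosing. It does not make dizzy placebo patients comparable with dizzy lasmiditan patients, because treatment changes who becomes dizzy. If any patient characteristic influences both the adverse event and the headache response, the groups are sorted differently in each arm. The within-group odds ratio then mixes drug effect with that sorting. The same applies to the non-dizzy group and so to the interaction test. Timing adds a second problem: with a 48-hour window, some patients are classified by an event that began after the 2-hour outcome on which they are analysed.

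What is at stake is how these outputs are read. An odds ratio, confidence interval and p-value produced with the primary model look like evidence on whether efficacy differs in patients who become dizzy or somnolent. They cannot answer that question.

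**Working it through.** **Plan's own figures.** The SAP gives no figure for SUB2 or SUB19. The arm sizes and rates used below come from its power table (SAP Section 5.2), so that table was checked first. Two-proportion power and simulation at two-sided 0.05 give T1 95.0% (stated 93.6%), T2 95.0% (94.9%), T3 92.2% (91.2%) and total 86.9% (85.6%). All are within two points.

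**Inputs from the documents**
- mITT: 190 placebo, 81 on 50 mg, 190 on 100 mg, 163 on 200 mg.
- Pain free at 2 h: 21.3% placebo, 38.8% on 200 mg. Overall odds ratio = (0.388/0.612)/(0.213/0.787) = 2.34.
- Pain relief at 2 h, placebo: 47.7%.
- Dizziness 15.4% to 17.2% and somnolence 5.1% to 6.0% on 100 and 200 mg (Protocol Section 3.2). The ends of these ranges are not assigned to doses.

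**Not in the documents:** any placebo rate for dizziness or somnolence. Values below are assumptions.

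**Step 1: group sizes.** Dizzy patients per 100 or 200 mg arm: 0.154 × 163 = 25 up to 0.172 × 190 = 33. Somnolent: 0.051 × 163 = 8 up to 0.060 × 190 = 11. Dizzy placebo patients at an assumed 1% to 4%: 190 × 0.01 = 1.9 up to 190 × 0.04 = 7.6, so 2 to 8.

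**Step 2: chance of no placebo responder among n dizzy placebo patients.** This is (1 − rate)^n, taking response as independent of dizziness.

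| n | No pain-free patient, 0.787^n | No patient with pain relief, 0.523^n |
|---|---|---|
| 2 | 62% | 27% |
| 4 | 38% | 7% |
| 6 | 24% | 2% |
| 8 | 15% | 0.6% |

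Placebo is the reference level and the test is a Wald test (SAP Section 5.6.1). With no placebo responder, none of the odds ratios in that group can be estimated. The SAP names no exact or penalised alternative.

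**Step 3: illustration of the bias, placebo against 200 mg.** Let U be a standard normal patient trait with logit P(dizzy) = a + U and logit P(pain free) = b + gU. The constants a and b are set per arm to give dizziness of 3% on placebo (assumed) and 17.2% on 200 mg, and pain freedom of 21.3% and 38.8%. The drug effect on the log-odds is then the same for every patient. Rates within the dizzy group are averages weighted by P(dizzy | U).

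| g | Dizzy: placebo, 200 mg, OR | Not dizzy: placebo, 200 mg, OR | Ratio of ORs |
|---|---|---|---|
| −1 | 10.5%, 25.2%, 2.87 | 21.6%, 41.6%, 2.58 | 1.11 |
| 0 | 21.3%, 38.8%, 2.34 | 21.3%, 38.8%, 2.34 | 1.00 |
| +1 | 37.2%, 53.7%, 1.96 | 20.8%, 35.7%, 2.11 | 0.93 |

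**Step 4: same model with no drug effect.** With 21.3% pain free in both arms and placebo dizziness of 2% to 5% (assumed), the true overall odds ratio is 1.00. The dizzy-group odds ratio runs from 0.82 to 1.19 and the non-dizzy one from 0.88 to 1.10. Both equal 1.00 only at g = 0, where dizziness and response share no cause.

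**Step 5: a different assumption.** If the trait acts only on drug, as exposure might (g = 0.5 to 1.0), the odds ratios are 3.30 to 4.29 (dizzy) and 2.18 to 2.05 (not dizzy). The ratio is then 3.30/2.18 = 1.51 up to 4.29/2.05 = 2.09. This is a difference by exposure that would be read as a difference by dizziness.

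**The case against.** The strongest reply is that little depends on these analyses. They are two of 21 subgroups, lie outside the T1–T2–T3 gatekeeping sequence, carry no multiplicity adjustment, and support no listed objective. That stands, and it limits the weight of the point.

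It can also be said that the distortion is modest. Under a shared trait the two odds ratios move in the same direction. A simplified two-arm Wald interaction test at the planned sizes, without the covariate, rejected in at most 2.7% of simulated trials at assumed placebo rates of 1%, 3% and 4%, counting non-estimable trials as no rejection. A reader might infer that the plan is bound to produce a false interaction. The documents do not support that: in this scenario the test is uninformative rather than falsely positive, and the larger contrast in step 5 needs a different assumption.

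Three further limits stand. The sparse placebo group rests on an assumed rate, is much milder for pain relief, and concerns only the group with the TEAE. One might say that these events are caused largely by the drug, but Protocol Section 5.4 supports only that they increase with lasmiditan and dose, which is all the argument needs. SUB21 is a precedent for format, not evidence that the authors saw this problem. Nor is it the only split that uses post-dose information. SUB17 does too, but is marked only for TEAEs, and the SUB3 menstrual window runs past the dosing day, though the documents do not suggest that treatment affects it.

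Finally, SAP Section 5.7.7.7 already summarises 2-hour disability and PGI-C descriptively among patients with dizziness. That shows a descriptive format is workable. It does not remove the tests in Section 5.8.

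**Conclusion.** The point holds. As written, Section 5.8 commits SUB2 and SUB19 to placebo-referenced odds ratios, p-values and a 0.05 interaction test in groups that treatment itself helps to form. That conclusion follows from the text and needs no assumed rate.

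The size does need assumptions. The figures in steps 3 to 5 are illustrations under a single latent trait and assumed placebo rates, and neither the size nor the direction of bias can be known from the documents. The risk that the dizzy-group odds ratio cannot be estimated depends on the assumed 1% to 4% placebo rate and on independence of dizziness and response. For somnolence, the expected 8 to 11 patients per 100 or 200 mg arm make the group smaller still, but its placebo count cannot be derived.

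A reader might infer that the trial's main conclusions are at risk. They are not: T1, T2 and T3 do not use these groups. This is a change that should be made to exploratory outputs, not a threat to the confirmatory analysis.

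**What to change.** In SAP Section 5.8 and Table LAIH. 5.6, exempt SUB2 and SUB19 from the model-based efficacy tests. For each efficacy column marked, report counts and response rates by arm, with no odds ratio against placebo, no p-value and no interaction test, as for SUB21. By the same reasoning, show treatment satisfaction as a distribution without the CMH test.

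If a comparison of patients with and without the TEAE is wanted, show it separately for each dose arm and label it descriptive and non-randomised. Pooling the lasmiditan arms would add confounding by dose, because the protocol says both efficacy and these TEAEs rise with dose.

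The cost is a short wording change and fewer outputs. The only loss is a set of p-values and odds ratios that have no randomised interpretation; all the descriptive information is kept.

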6.2. Inclusion Criteria

Patients are eligible to be included in the study only if they meet all of the following criteria at Visit 1:

Type of Patient and Disease Characteristics

- [1] Patients with migraine with or without aura fulfilling the IHS diagnostic criteria 1.1 and 1.2.1 (International Classification of Headache Disorders [ICHD]-2).
- [2] History of disabling migraine for at least 1 year.
- [3] MIDAS score ≥ 11 .
- [4] Migraine onset before the age of 50 years.
- [5] History of 3 – 8 migraine attacks per month and <15 headache days per month during the past 3 months.
- [6] Male or female, aged 18 years or above.
- [7] Able and willing to complete an eDiary to record details of the migraine attack treated with study drug.

Patient Characteristics

- [8] *Women of child-bearing potential* must agree to use a highly effective method of contraception such as combination oral contraceptives or intrauterine devices approved in Japan, or sterile partner during clinical trial period and until 30 days after the last dose of study medication and to report occurrences of pregnancy or suspected pregnancy to the investigator immediately.

Women of child-bearing potential who are abstinent (if this is complete abstinence, as their preferred and usual lifestyle) or in a same-sex relationship (as part of their preferred and usual lifestyle) must agree to either remain abstinent or stay in a same-sex relationship without sexual relationships with males. Periodic abstinence (for example, calendar, ovulation, symptothermal, post-ovulation methods), declaration of abstinence just for the duration of a trial, and withdrawal are *not* acceptable methods of contraception.

Women not of child-bearing potential may participate and include those who are:

- Infertile due to surgical sterilization (hysterectomy, bilateral oophorectomy, or tubal ligation), congenital anomaly such as mullerian agenesis; or
- Post-menopausal – defined as either
 - a woman between 40-50 years of age with an intact uterus, not on hormone therapy, who has had
 - cessation of menses for at least 1 year, and
 - a follicle-stimulating hormone >40 mIU/mL;
 - a woman at least 50 years of age with an intact uterus, not on hormone therapy, who has had either
 - cessation of menses for at least 1 year, or
 - at least 6 months of spontaneous amenorrhea with a follicle-stimulating hormone >40 mIU/mL; or

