5.6.2. Sensitivity Analysis

As sensitivity analysis for [T1] (primary), [T2], [T3] (key secondary), and MBS, following method will be conducted:

- The same analysis will be conducted based on ITT and PPS
- “non-responder” patients due to missing data (post baseline) will be excluded from (Reference Section [5.4.1](#)) mITT population

In addition, [T1] [T3] analysis will be conducted for patients who are in mITT and who have not vomited up to 2 hours. That is, eliminate patients who recorded vomiting at least once between 0 hour to 2 hours (inclusive), recorded in the eDiary.

In addition, as sensitivity analysis for [T1], separate subgroup models specified below will be fitted:

- [1] Previous triptan response (none + poor (0-1), good (2-3))
- [2] Baseline disability severity ('need complete bed rest', the others)
- [3] Baseline headache severity (moderate or severe)
- [4] Baseline associate symptom (with/without nausea)
- [5] Menstrual period (-2d before cycle to total 5 days)
- [6] Body weight (continuous variable)
- [7] Age (continuous variable)
- [8] Gender
- [9] Baseline migraine attacks (<=5 attacks per month, > 5 attacks per month)
- [10] Time of dose relative to onset of migraine (dosing time <= 1 hour, dosing time > 1 hour)
- [11] Duration of migraine history (<=median, > median)

The definition of [1] and [5] are the same as the one specified in Section [5.8](#).

The model term include treatment, baseline usage of preventive medications to reduce the frequency of migraine (Yes/No), subgroup, and treatment-by-subgroup interaction.

The response rate for each arm, along with 95% confidence interval, will be estimated based on LSMeans.

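### The menstrual subgroup (SUB3 and sensitivity model [5]) sets women in the menstrual window against everyone else, men included, so its between-group contrast cannot be read as menstrual timing if sex or age modifies the drug effect

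*SAP*

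**What the plan says.** Table LAIH. 5.6 of the SAP lists SUB3 as "Menstrual related (yes/no") with mITT as its population and nothing further. The definition below the table reads "Group 1: Female with menstruation at least one day in" the five days running from Day −2 to Day 3, and then "Group 2: Otherwise". Day 1 is the day of dosing.

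Where the SAP wants a narrower population, the same table says so. For SUB1 the entry is "mITT and patients who has triptan experience in lifetime". SUB3 has no such limit.

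Protocol Section 6.2 admits "Male or female, aged 18 years or above" with no upper age limit, and lets surgically sterile and post-menopausal women take part.

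For proportions, Section 5.8 fits a logistic model with treatment, preventive use, subgroup and their treatment interaction, and states "The p-value for treatment-by-subgroup interaction will be displayed", with a two-sided level of 0.05. SUB3's outputs are demographics, TEAEs by preferred term, and time courses to 48 hours for pain freedom, pain relief, MBS freedom and disability.

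Section 5.6.2 repeats the factor as a supplementary model for T1, in the words "5] Menstrual period (-2d before cycle to total 5 days", and refers to Section 5.8 for its definition.

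**The concern.** Group 1 contains no men and no women who have stopped menstruating. Every such patient is in Group 2, together with menstruating women treated outside the window. Group membership is therefore tied to sex and to menopausal age by construction, and the model adjusts for neither.

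A reader of a table labelled as menstrual-related, yes against no, will take a difference in drug effect between the rows as something about the menstrual attack. If the drug worked differently in men or in older women, that difference would appear in the same place and the table could not tell the two apart. What is at stake is the reading of an exploratory result, not a confirmatory conclusion.

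**Working it through.** **Plan figures used.** The documents give no figure for SUB3. The planned mITT size (624, split 190:81:190:163) and the assumed pain-free rates (21.3%, 28.6%, 31.4%, 38.8%) come from SAP Section 5.2. As a check on those inputs, simulating the three gatekept tests gives power of 95.2%, 95.0% and 92.2%, and 86.9% jointly. The plan states 93.6%, 94.9%, 91.2% and 85.6%. These agree within 2 points, and the plan's power is not in dispute.

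**Composition of Group 2 (illustration).** The female-to-male ratio of 3.6 is the Japanese prevalence ratio in Protocol Section 3.2, so using it for enrolment is an assumption. Also assumed are *p*, the share of women who are post-menopausal (10% to 20%), and *g*, the share of the remaining women with menstruation in the window (20% to 30%).

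- Women: W = 3.6/4.6 = 0.783. Men: M = 1/4.6 = 0.217.
- Group 1 share: G1 = W(1 − p)g. Group 2 share: 1 − G1.
- Men in Group 2: M/(1 − G1). Men plus post-menopausal women: (M + Wp)/(1 − G1).

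| p | g | Group 1 of 624 | Group 2 of 624 | Men in Group 2 | Men + post-menopausal |
|---|---|---|---|---|---|
| 10% | 20% | 88 | 536 | 25.3% | 34.4% |
| 10% | 30% | 132 | 492 | 27.6% | 37.5% |
| 20% | 20% | 78 | 546 | 24.9% | 42.7% |
| 20% | 30% | 117 | 507 | 26.8% | 46.0% |

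With wider inputs (ratio 3.6 to 5.0, p 5% to 20%, g 20% to 40%), men are about 19% to 31% of Group 2, and men plus post-menopausal women about 25% to 50%.

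**What this could do to the interaction.** Take a deliberately extreme case: no menstrual effect at all, women at the planned rates, and men at 21.3% on every arm. With p = 10% and g = 32%, Group 1 is about 141 patients and men are 28.1% of Group 2.

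- Group 2 rate on 200 mg: 0.281 × 21.3% + 0.719 × 38.8% = 33.9%. Group 1 rate: 38.8%.
- Log odds ratio against placebo: Group 1, logit(0.388) − logit(0.213) = 0.85. Group 2, logit(0.339) − logit(0.213) = 0.64.
- Spurious interaction: 0.85 − 0.64 = 0.21.

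Simulation (preventive-use term omitted; 3,000 runs at N = 624 and 800 runs at ten times N) agrees:

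| | All mITT, as planned | Women who still menstruate only |
|---|---|---|
| Mean 200 mg interaction, log odds ratio, N = 624 | +0.22 | +0.01 |
| Rejection, 3-df interaction test, N = 624 | 4.2% | 3.6% |
| Rejection, 200 mg contrast, N = 624 | 5.9% | 4.3% |
| Rejection, 3-df test, ten times N | 17% | 5% |
| Rejection, 200 mg contrast, ten times N | 25% | 5% |

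When men respond exactly as women do, the all-mITT version shows a mean interaction of +0.01, so the bias disappears.

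**The case against.** The strongest reply is about weight. SUB3 is one of 21 subgroups and item [5] one of 11 supplementary models. None is in the gatekeeping sequence, and none is adjusted for multiplicity. Demographics are tabulated for SUB3, so the imbalance in sex and age will be visible, and both factors have their own interaction analyses (SUB15, SUB16, items [7] and [8]). The SAP never says that SUB3 is meant to isolate menstrual timing. If the aim is only to see whether the drug works in menstrual-related attacks, Group 1 against placebo answers it. In the illustration, 54% to 66% of Group 2 are women who are neither post-menopausal nor in the window. Protocol Section 3.1 also reports no consistent sex difference in pharmacokinetics, and no sex difference in TEAE frequency among Japanese volunteers.

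Most of this stands, and it is why the point is minor. Two parts do not remove it. Tabulating an imbalance, or testing sex and age one at a time elsewhere, does not adjust the SUB3 contrast. And the volunteer data concern exposure and tolerability, not efficacy in an attack.

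A reader might go further and infer that the planned interaction test will produce false positives. The calculation does not support that: at 624 patients the rejection rate stays near 5% even if men get no benefit at all. A reader might also infer that the contrast is biased whatever the truth. It is biased only if sex or age modifies the drug effect, and the documents neither show nor exclude that.

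**Conclusion.** The point holds as a minor one. It follows from the wording of SUB3 and the model terms alone: the yes/no contrast is mixed with sex and menopausal age, and nothing in the model separates them. If either modifies the drug effect, the interaction p-value and the paired rates are not a measure of menstrual timing. Placebo comparisons within each group remain valid, and the primary and key secondary tests do not change.

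The shares of 25% to 28% and 34% to 46% rest on three assumed inputs and show only that the mixing need not be trivial. The shift of about 0.2 in the log odds ratio rests on the extreme assumption of no drug effect in men and should be read as that scenario, not as a forecast. At the planned size the harm is an estimate that is hard to interpret, not an inflated error rate.

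**What to change.** For the between-group contrast in SUB3 and in item [5]:

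- Limit the population to mITT women with recorded menstrual periods, taken from the Visit 2 and Visit 3 dates or the paper diary. Both are already in the Schedule of Activities.
- Group 1 is those treated inside the window; Group 2 is those treated outside it.
- Exclude women whose missing dates prevent classification, and report how many there are. SUB3 does not say where they go.
- Do not use Table LAIH. 5.7 to decide who still menstruates. It classes a woman with FSH above 40 mIU/mL as post-menopausal even when she answers yes to the menstrual period question.
- Reword item [5] to the dosing-anchored window of SUB3. Its present wording is anchored to the cycle, although it defers to Section 5.8.

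The all-mITT version can stay as a descriptive display.

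No new data are needed, but the change takes more than one line of the SAP. The cost is precision. In the four scenarios above, Group 2 becomes 624 × W(1 − p)(1 − g), about 352, 308, 313 and 274 patients, in place of 536, 492, 546 and 507. Taking the variance of the contrast as proportional to 1/n1 + 1/n2 (same arm split and same per-patient variance in both groups), its standard error rises by about 4% to 8%. For example, with p = 10% and g = 20%, √[(1/88 + 1/352)/(1/88 + 1/536)] = 1.04. Age differences among menstruating women would remain.
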